2.3.2. Risks for Study Participation

2.3.2.1. Known Risks

Injection site reactions were the most frequently observed AEs assessed as related to JNJ-3989 by the investigator.

The side effect profile of PegIFN- α 2a is well established and includes, but is not limited to, neuropsychiatric, autoimmune, ischemic, ophthalmologic, hematological, and infectious disorders. Exacerbations of hepatitis during hepatitis B therapy are common and characterized by transient and potentially severe increases in serum ALT. Marked increases in ALT were sometimes accompanied by bilirubin elevation and other liver test abnormalities. In many, but not all cases, these disorders resolve after stopping PegIFN- α 2a therapy. For a full list of known risks for PegIFN- α 2a, refer to the respective prescribing information and Summary of Product Characteristics.

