6.5.1. NA Treatment Completion

All participants will receive the last dose of JNJ-3989 at Week 24 and the last dose of PegIFN- α 2a at Week 23 (Arms 1 and 2) or Week 11 (Arm 3). They will start the FU Period after the Week 24 visit. If all of the following NA treatment completion criteria are met based on the Week 24 results, treatment with NA will be stopped at the next scheduled visit (ie, FU Week 2):

- The participant has ALT <3x ULN, AND
- The participant has HBV DNA <60 IU/mL at Week 24 and HBV DNA <LLOQ at the previous visit, or HBV DNA <LLOQ at Week 24, AND
- The participant is HBeAg-negative, AND
- The participant has HBsAg <100 IU/mL.

Note: Participants who are close to meeting the protocol-defined NA treatment completion criteria with the Week 24 results, and do meet the criteria based on the FU Week 2 results may be allowed to stop NA at FU Week 4, after consultation with the Sponsor. In case of ALT elevation \geq 3x ULN at Week 24, the investigator must consider different potential causes of increased ALT to ensure appropriate work up and management as needed. If the ALT elevation is unrelated to HBV activity and/or <3x ULN by FU Week 2, NA completion may be considered at the discretion of the investigator and in consultation with the sponsor.

Participants who do not meet the above criteria based on the Week 24 or FU Week 2 results should continue NA treatment during the 48-week FU Period.

Participants who meet the above-mentioned NA treatment completion criteria will be monitored closely during the 48-week FU Period with a study visit at least once every 4 weeks. NA treatment should be re-started in accordance with the NA re-treatment criteria (see Section [6.5.2](#), NA Re-treatment Criteria During Follow-up, for more details).

The investigator should consider to re-start NA treatment per local standard of care at the EOS visit (Follow-up Week 48) for participants who met the NA treatment completion criteria based on the Week 24 (or FU Week 2) results, who did not re-start NA treatment during the follow-up phase, and who did not achieve and maintain HBsAg seroclearance. NA will not be provided by the sponsor after the final study visit.

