8.3.6.2. Intervention-emergent ALT/AST Elevations

Elevated liver enzyme activity can be triggered by the underlying HBV disease as well as by the study intervention.

Management of intervention-emergent ALT/AST elevations is presented graphically in Section [10.7](#), Appendix 7: Intervention-emergent ALT/AST Elevations, and is described below.

Any intervention-emergent elevation of ALT and/or AST $\geq 3x$ ULN and $\geq 3x$ nadir (ie, lowest value during study participation) should trigger an assessment of confounding factors (alcohol intake, change in concomitant medication, and comorbidities) and should trigger a confirmatory study visit to repeat laboratory testing of AFP, ALT, AST, ALP, bilirubin (total and direct), INR, albumin, and HBV DNA. Additional tests should be considered based on clinical judgement (refer to Section [10.7](#), Appendix 7: Intervention-emergent ALT/AST Elevations). This confirmatory visit should be scheduled as soon as possible within 7 days of the receipt of the initial ALT/AST results. In case the repeat laboratory testing shows an isolated ALT/AST elevation (ie, with stable albumin, bilirubin [total and direct], and INR) the participant may continue study intervention. In case of confirmed ALT elevation $>1,000$ U/L and $\geq 3x$ the baseline value, JNJ-3989 (and PegIFN- $\alpha 2a$ if applicable) should be discontinued. In both cases, NA treatment should be continued. The participant will be monitored (laboratory testing of AFP, ALT, AST, ALP, bilirubin [total and direct], INR, albumin, and HBV DNA) on a weekly basis or more frequently until ALT and AST levels have returned to $<5x$ ULN and HBV DNA is $<20,000$ IU/mL. Additional PBMC and AFP samples may be taken in case of ALT flares, upon discussion with the Sponsor, which may require an unscheduled visit.

If the ALT and/or AST level is $\geq 3x$ ULN and $\geq 3x$ nadir and is associated with any of the following laboratory results or clinical symptoms:

- INR ≥ 1.5 , OR
- direct bilirubin $> 1.5x$ ULN, OR
- serum albumin < 3.0 g/dL, OR
- ascites, hepatic encephalopathy, or liver-related symptoms (eg, severe fatigue, nausea, vomiting, right upper quadrant pain in the absence of an alternative medical explanation), OR
- other indication of reduced liver function,

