ISR	injection site reaction
KPD	kinetic pharmacodynamic model
LLN	lower limit of normal
LLOQ	lower limit of quantification
MDSC	myeloid-derived suppressor cell
MoA	mode of action
MRI	magnetic resonance imaging
MRU	medical resource utilization
NA	nucleos(t)ide analog
NIMP	non-investigational medicinal product
NK	natural killer
NOAEL	no observed adverse effect level
PBMC	peripheral blood mononuclear cell
PD	pharmacodynamic(s)
PegIFN- α 2a	pegylated interferon alpha-2a
pgRNA	pre-genomic ribonucleic acid
PK	pharmacokinetic(s)
PoC	proof of concept
Q4W	every 4 weeks
QW	weekly
QD	once daily
QTcF	QT interval corrected for heart rate according to Fridericia's formula
RBC	red blood cell
rcDNA	relaxed circular deoxyribonucleic acid
RNAi	ribonucleic acid interference
SAE	serious adverse event
SAP	Statistical Analysis Plan
SD	standard deviation
SDM	site-directed mutant
SE	standard error
siRNA	small interfering ribonucleic acid
$t_{1/2\text{term}}$	terminal half-life
T4	thyroxine
TAF	tenofovir alafenamide
TEAE	treatment-emergent adverse event
t_{max}	time to reach C_{max}
TND	target not detected
TNF	tumor necrosis factor
TSH	thyroid stimulating hormone
WBC	white blood cell

Definitions of Terms

ALT/AST nadir	Lowest ALT/AST value during study participation
End of study intervention (EOSI)	Time of the last administration of study intervention
Functional cure (FC)	HBsAg seroclearance at 24-weeks after EOSI
HBsAg or HBeAg seroclearance	HBsAg or HBeAg negativity, respectively, based on the assay used
HBsAg or HBeAg seroconversion	HBsAg or HBeAg negativity and anti-HBs or anti-HBe antibody positivity, respectively
IC ₅₀	half maximal inhibitory concentration
Study intervention	JNJ-73763989 (JNJ-3989), NA (either ETV, tenofovir disoproxil, or TAF), and PegIFN- α 2a
Virologic breakthrough	Confirmed on-treatment HBV DNA increase by $>1 \log_{10}$ IU/mL from nadir or confirmed on-treatment HBV DNA level >200 IU/mL in participants who had HBV DNA level $<$ LLOQ of the HBV DNA assay.

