#### **5.4.1.1.14. Flares**

The criteria based on blood markers/lab tests for each of the flare types are defined as below.

**1. Virologic flare** is defined as follows:

Virologic flare will be assessed only for those participants who are off-treatment.

The start of a confirmed virologic flare is defined as the first date of two consecutive visits with HBV DNA  $>200$  IU/mL. The end date of the same confirmed virologic flare is defined as the first date when HBV DNA value returns to  $\leq 200$  IU/mL or the date of NA treatment restart, whichever

comes first. Each virologic flare will be categorized based on the confirmed (i.e. two consecutive values) peak HBV DNA above any of the three thresholds within the start and end date of that flare as follows: 20,000 IU/mL 2,000 IU/mL and 200 IU/mL.

- 1 (Yes) = confirmed\*\* HBV DNA > peak threshold.
- 0 (No) = at least one off-treatment HBV DNA measurement available and not meeting the criteria of confirmed HBV DNA > peak threshold.
- 2 (Not applicable) = no off-treatment HBV DNA quantitative measurements available.

**2. Off-treatment Biochemical flare** is defined as follows:

The start date of a confirmed off-treatment biochemical flare is defined as the first date of two consecutive visits with ALT and/or AST  $\geq 3x$  ULN and  $\geq 3x$  off-treatment nadir (i.e. lowest value observed during off-treatment period up to the time point of meeting the biochemical flare criteria) while the participant does not receive any of the study interventions. The end date of the same off-treatment biochemical flare is defined as the first date when there is a 50% reduction from the peak ALT and/or AST level &  $< 3x$  ULN.

- 1 (Yes) = confirmed\*\* ALT and/or AST  $\geq 3x$  ULN and  $\geq 3x$  nadir (i.e. lowest value observed up to the start of the flare)
- 0 (No) = otherwise

**3. On-treatment Biochemical flare** is defined as follows:

The start date of a confirmed on-treatment biochemical flare is defined as the first date of two consecutive visits with ALT and/or AST  $\geq 3x$  ULN and  $\geq 3x$  on-treatment nadir (i.e. lowest value observed on-treatment period up to the time point of meeting the biochemical flare criteria) while the participant receives any of the study interventions. The end date of the same on-treatment biochemical flare is defined as the first date when there is a 50% reduction from the peak ALT and/or AST level &  $< 3x$  ULN, regardless of stopping the study interventions.

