- 1 (Yes) = confirmed\*\* ALT and/or AST  $\geq 3x$  ULN and  $\geq 3x$  nadir (i.e. lowest value observed up to the start of the flare)
- 0 (No) = otherwise

**4. Clinical flare** is defined as follows:

A clinical flare occurs either when a virologic flare and biochemical flare overlap in time or when a biochemical flare starts within 4 weeks following the end of a virologic flare. The start date of a clinical flare is defined as the minimum start date of the virologic flare and the biochemical flare. The end date of a clinical flare is defined as the maximum end date of the virologic flare and biochemical flare, i.e., the later date of HBV DNA returns to  $\leq 200$  IU/mL and 50% reduction from the peak ALT and/or AST level.

- 1 (Yes) = confirmed\*\* HBV DNA > peak threshold and confirmed\*\* ALT and/or AST  $\geq 3x$  ULN and confirmed\*\*  $\geq 3x$  nadir (i.e. lowest value during study participation).

- 0 (No) = otherwise

\*\* Confirmed means that the criterion should be fulfilled at 2 or more consecutive time points or at the last observed time point.

The virologic and clinical flares will be assessed only off-treatment, while biochemical flares will be identified on-treatment and off-treatment. On-treatment virologic flares are described as virologic breakthrough in Section 5.4.1.1.13. On-treatment will be defined as the time period in which the participant receives any of the study interventions. Off-treatment will be defined as the period after stopping all study interventions (including NA).

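### SAP 5.4.1.1.14 uses three different ALT/AST nadirs for flares, and the off-treatment one can set a higher bar than the protocol's nadir, leaving some flares undated or uncounted

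*SAP*

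**What the plan says.** **Protocol.** Appendix 1 (Section 10.1) defines the ALT/AST nadir as "Lowest ALT/AST value during study participation". Section 8.3.6.2 uses the same nadir in its management rule: an elevation of at least 3x ULN and at least 3x "nadir (ie, lowest value during study participation) should trigger an assessment of confounding factors". Nothing restarts the nadir when treatment stops.

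**SAP 5.4.1.1.14.** Three wordings appear:

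- *Start-date definitions.* The off-treatment biochemical flare uses the "lowest value observed during off-treatment period up to the time point of meeting the biochemical flare criteria". The on-treatment one uses the "lowest value observed on-treatment period up to the time point of meeting the biochemical flare criteria".
- *Yes/No lines for biochemical flares.* The nadir is the lowest value before the flare begins, with no limit to a treatment period.
- *Yes/No line for clinical flares.* The nadir is study-wide: "i.e. lowest value during study participation".

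The same section starts the off-treatment period only when every study intervention, NA included, has stopped. SAP Appendix 2 declares no departures from the analyses planned in the protocol.

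**NA completion (Protocol 6.5.1).** One criterion, judged on the Week 24 result, reads "The participant has ALT <3x ULN, AND". NA then stops at FU Week 2, or at FU Week 4 for those who qualify on FU Week 2 results. A note allows completion to be considered at 3x ULN or above when the elevation is unrelated to HBV activity.

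**The concern.** A flare must reach 3x ULN and also 3x the nadir. If the nadir is taken only from off-treatment samples, a participant who stops NA with raised ALT starts from a high reference value, and the second condition becomes the binding one. A rise that clearly qualifies against the participant's own study low may then fail.

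The frequency of virologic and/or biochemical flares in participants who met the NA completion criteria is a secondary endpoint (Protocol Section 3). The same derivation feeds time to first flare (SAP 5.4.1.3.5), flares followed by NA re-treatment or HBsAg seroclearance (SAP 5.4.2.1.14), the flare summaries for the Data Review Committee (SAP Table 10), and clinical flares, which by definition need a biochemical flare with dates. With three nadirs in one section, two programmers could follow the SAP faithfully and report different counts.

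**Working it through.** The documents state no effective flare bar, so there is no figure to reproduce. The check is the arithmetic of the two conditions, with ALT in multiples of ULN.

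**Inputs.** The flare condition is ALT and/or AST at least 3x ULN and at least 3x nadir (SAP 5.4.1.1.14; Protocol 8.3.6.2). ALT at NA completion is below 3x ULN (Protocol 6.5.1). Entry ALT is below 2.0x ULN, including at screening (Protocol 5.1, criterion A03).

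**Formula.** Bar = max(3, 3 x nadir).

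**Direction.** The study-wide low is a minimum over all samples, and the off-treatment low is a minimum over a subset of them. The first can therefore never exceed the second, and the SAP start-date bar is never below the protocol bar. The start-date rule can drop flares but cannot add any.

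**Size.** If the first off-NA value is also the lowest off-treatment value before the flare, and the study low is at or below 1.0:

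| First off-NA ALT (x ULN) | Bar, SAP off-treatment start-date rule | Bar, study-wide nadir |
|---|---|---|
| 1.0 | max(3, 3.0) = 3.0 | 3.0 |
| 1.5 | 3 x 1.5 = 4.5 | 3.0 |
| 2.0 | 3 x 2.0 = 6.0 | 3.0 |
| 2.5 | 3 x 2.5 = 7.5 | 3.0 |
| 2.99 | 3 x 2.99 = 8.97 | 3.0 |

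With a study low of 1.5 the study-wide bar is 4.5. If screening counts as study participation, the entry limit keeps that bar below 3 x 2.0 = 6.0.

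**One participant under each wording (assumed values).** Study low 0.5; ALT below 3 throughout treatment; first off-NA value 2.0; then 5.5 and 5.8 at consecutive visits.

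- *Start-date rule:* 5.5/2.0 = 2.75 and 5.8/2.0 = 2.9. Both fall short of 3, so there is no start date.
- *Biochemical Yes/No line, nadir taken over all earlier samples:* 5.5/0.5 = 11, so Yes. The line refers to a flare start that the start-date rule does not supply.
- *Clinical flare line:* 5.5/0.5 = 11, so the ALT part is met. Yet the definition above it needs a dated biochemical flare, and there is none.
- *On-treatment flare:* none, because ALT stayed below 3x ULN on treatment.

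Both values exceed 5x ULN, the ALT level named in one of the protocol's NA re-treatment criteria (Section 6.5.2).

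**When the rules agree.** The off-treatment nadir is a running minimum. Had the first off-NA value been 1.0, the bar would be 3.0 under both rules and the rise to 5.5 would count under either.

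**The case against.** Four objections have force.

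- *The Yes/No line may govern incidence.* It carries no period limit, and read that way the participant above is counted. This stands, so loss from the flare count depends on what is programmed. It does not rescue the endpoint: the participant would then be a Yes without a date, and time to first flare would still miss the event.
- *An off-treatment nadir can be a deliberate choice, because it isolates the rise after NA stops.* It has merit. With a study low of 0.5, 2.8 at NA stop and then 3.1 twice, a study-wide nadir yields an off-treatment flare (3.1/0.5 = 6.2), although ALT rose only about 11% since stopping (3.1/2.8 = 1.11). But the SAP does not state this rationale, and it applies a different nadir in the lines directly below.
- *The protocol lists biochemical flares as an endpoint without defining them and leaves detail to the SAP.* This stands as far as it goes: whether Appendix 2 is wrong is arguable. The contradiction within the SAP section remains.
- *Safety is covered elsewhere.* This also stands. The protocol's management rule keeps the study-wide nadir, its re-treatment criteria use no nadir, the Independent Flare Expert Panel adjudicates ALT flares, and toxicity grades are summarised separately. The point concerns endpoint counts and times, not patient monitoring.

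**Conclusion.** The concern holds as a contradiction in SAP 5.4.1.1.14 that should be resolved before the flare endpoints are programmed. Under the off-treatment start-date rule the bar is three times an unsettled first off-NA value, up to just under 9x ULN when that value is below 3x ULN. That is an upper illustration, not a typical case, and not a strict cap: completion rests on the Week 24 result while NA stops later, an exception permits higher ALT, and no AST limit is set. The documents give no distribution of ALT at NA stop, so the number of participants affected is unknown.

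Three stronger readings are tempting, and the documents do not support them.

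- *That the nadir restarts at every analysis phase.* The split is on-treatment versus off-treatment. Participants who stay on NA in follow-up remain on-treatment and have no restart.
- *That on-treatment flares are lost in the same way, because a low baseline is ignored.* SAP Table 4 places the pre-dose baseline inside the treatment period, and nothing excludes it from the on-treatment nadir.
- *That Arms 1 and 2 lose more flares than Arm 3, because PegIFN ends at Week 23 rather than Week 11.* No ALT data by arm are given. The first scheduled sample after an NA stop at FU Week 2 is at FU Week 4 (study Week 28), 28 - 23 = 5 weeks after the last dose in Arms 1 and 2. The protocol's statement that "Exacerbations of hepatitis during hepatitis B therapy are common and characterized by transient and potentially severe increases in serum ALT" concerns events during therapy, and the same section says that many, though not all, such disorders resolve after PegIFN stops.

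**What to change.** In SAP 5.4.1.1.14, define one nadir for all biochemical and clinical flares: the lowest ALT/AST during study participation, baseline included, up to the start of the flare. Remove the on-treatment and off-treatment nadirs from the start-date definitions, and assign each flare to on- or off-treatment by its start date alone. Use the same nadir in the Yes/No lines, so that every flare coded Yes has a date. State whether screening values count, since the protocol definition does not say.

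If the sponsor wants to isolate the rise after NA stops, keep an off-treatment-nadir version as a labelled supplementary summary and list it in SAP Appendix 2.

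The cost is a wording change and one derivation, with no new data. The downside is that counts may rise, and some elevations carried over from before NA stopped may be counted as off-treatment flares. The supplementary summary would show how many.

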## **5.4.1.2. Continuous Endpoints**

### **5.4.1.2.1. HBsAg, HBeAg, HBV DNA and ALT**

Actual values (original unit and  $\log_{10}$  transformed values), changes from baseline ( $\log_{10}$  transformed values) and change from RTs over time in HBsAg, HBeAg, HBV DNA and ALT (actual values only) will be evaluated.

Change from baseline is defined as the value at a given time point minus baseline value.

The change from baseline value to the nadir (i.e. maximum decrease for each participant) in HBsAg, HBeAg, and HBV DNA will be evaluated at 3 intervals: on-treatment nadir (first 24 weeks), during follow-up nadir, and entire study nadir.

## **5.4.1.3. Time to Event Endpoints**

### **5.4.1.3.1. Time to First HBsAg Seroclearance**

Time to HBsAg seroclearance is defined as the number of days between the date of first study intervention intake and the date of the first occurrence of HBsAg seroclearance (i.e. the date of the first HBsAg seroclearance – the date of first study intervention intake + 1). The participants who withdrew early from the study before achieving HBsAg seroclearance or who did not achieve HBsAg seroclearance will be censored at the last available HBsAg assessment.

Time to HBsAg seroclearance will be also analyzed considering the participants who were retreated with NA before achieving HBsAg seroclearance as censored at the date of NA retreatment.

In addition, time to the first occurrence of the following events (i.e. the date of the first occurrence of the event – the date of first study intervention intake + 1) will be analyzed:

- HBsAg <100 IU/mL
- HBsAg decline  $\geq 1.0 \log_{10}$  IU/mL
- HBsAg decline  $\geq 2.0 \log_{10}$  IU/mL
- HBsAg decline  $\geq 3.0 \log_{10}$  IU/mL

Time to the first occurrence of the events above will be also analyzed considering the participants who were retreated with NA before achieving the event as censored at the date of NA retreatment.

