#### **5.4.1.3.2. Time to First HBsAg Seroconversion**

Time to first HBsAg seroconversion is defined as the number of days between the date of first study intervention intake and the date of the first occurrence of HBsAg seroclearance and appearance of anti-HBs antibodies (i.e. the date of the first HBsAg seroclearance and anti-HBs antibodies – the date of first study intervention intake + 1). The participants who withdrew early from the study before achieving HBsAg seroclearance and anti-HBs antibodies or who did not achieve HBsAg seroclearance and anti-HBs antibodies will be censored at the last available anti-HBs antibodies assessment.

Time to first HBsAg seroconversion will be the participants who were retreated with NA before achieving HBsAg seroclearance and anti-HBs antibodies will be censored at the date of NA retreatment.

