#### **5.4.2.3. Time to Event Endpoints**

The Kaplan-Meier method will be used to estimate and plot the cumulative incidence by each intervention arm. The log-rank test will be performed to compare between the intervention arms. The median time with 90% CI will be estimated using Kaplan-Meier method. To explore the impact of selected baseline factors in addition of study intervention, the survival probabilities will be estimated based on a stratified Cox regression model including study intervention arm, and each baseline factor at a time with the intervention arm-by-baseline factor interaction term. The strata in the stratified Cox model are the 2 randomization stratification factors to allow for a separate baseline hazard for each level of those factors. The interaction between study intervention arm and baseline/disease characteristic will be explored graphically.

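### In the additional time-to-event analyses that censor at NA re-treatment, the Kaplan-Meier curve is labelled cumulative incidence but equals or exceeds the probability of reaching the event before NA restart

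*SAP*

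**What the plan says.** SAP 5.4.1.3.1 gives two analyses of time to HBsAg seroclearance. Both measure "the number of days between the date of first study intervention intake and the date of the first occurrence of HBsAg seroclearance".

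- **First-listed analysis.** Participants who withdrew early or "who did not achieve HBsAg seroclearance will be censored at the last available HBsAg assessment". NA re-treatment is not a censoring event here.
- **Additional analysis.** A second version, introduced as one that is also to be run, takes "the participants who were retreated with NA before achieving HBsAg seroclearance as censored at the date of NA retreatment". The same additional rule is given for HBsAg <100 IU/mL and for declines of at least 1, 2 and 3 log10 IU/mL.

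For seroconversion, SAP 5.4.1.3.2 first defines a version censored at the last anti-HBs assessment. It then adds a sentence that does not parse: "Time to first HBsAg seroconversion will be the participants who were retreated with NA before achieving HBsAg seroclearance" and anti-HBs antibodies will be censored at re-treatment. SAP 5.5.1.3 repeats the additional rule for HBV RNA, HBcrAg, anti-HBs and anti-HBe, and 5.5.2.3 sends those endpoints to the methods of 5.4.2.3.

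Those methods read: "The Kaplan-Meier method will be used to estimate and plot the cumulative incidence by each intervention arm". For the arms, "The log-rank test will be performed to compare between the intervention arms". A stratified Cox model is added for baseline factors. No competing-risk estimator is named.

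**The concern.** The additional variant exists to take NA restart into account: its natural reading is the probability of reaching the event before NA is restarted. A participant who restarts NA can no longer have that outcome. Censoring removes the participant from the risk set and implicitly assigns them the later clearance rate of those still at risk. A curve built this way is not a cumulative incidence.

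Independent censoring is also doubtful. Under Protocol 6.5.2, restart is prompted by HBV DNA, ALT, HBeAg seroreversion or signs of falling liver function, and Protocol 4.2 says that restarting too early may lower the chance of functional cure. Re-treatment and outcome are therefore linked in the sponsor's own reasoning.

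The variant also disagrees with the SAP's binary rules. Under 5.4.1.1.4.2 and 5.4.1.1.5 a restarted participant is not a responder. At stake is a supplementary curve that could be read beside those binary results and show a higher figure for what looks like the same thing.

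**Working it through.** The documents state no event rate, re-treatment rate or power for these endpoints, so there is no figure of the plan's own to reproduce.

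**Estimators.** At each time *j*, let *d* be clearances and *n* the number at risk, with re-treated participants removed from *n* in both methods.

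- 1-KM = 1 − ∏(1 − *d*/*n*). Equivalently, it sums *K* × *d*/*n*, where *K* is the Kaplan-Meier probability just before *j* of not having cleared.
- Aalen-Johansen sums *S* × *d*/*n*, where *S* is the probability just before *j* of having neither cleared nor been re-treated.

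The *d*/*n* terms are identical and *K* is never below *S*. So 1-KM is never below Aalen-Johansen. The two are equal if all clearances precede all re-treatments, and 1-KM is strictly higher once a clearance follows a re-treatment. With no other censoring, Aalen-Johansen is simply total clearances divided by the number in the arm.

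**Inputs from the documents.** 34 participants per arm, and 48 weeks of follow-up from Week 24 (SAP 1.2).

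**Assumed inputs.** 0 or 2 on-treatment clearances, 1 to 5 follow-up clearances, 2 to 15 re-treatments per arm, a grid of 12 four-week steps, no other censoring, and three timing patterns.

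**Worked cases.**

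- *Even timing, 3 follow-up clearances, 10 re-treatments.* Each step has 3/12 = 0.25 clearances, and *n* falls by 13/12 per step, from 34 to 22.08 at the last step. The product of the twelve terms (1 − 0.25/*n*) is 0.896, so 1-KM is 10.4%. Aalen-Johansen is 3/34 = 8.8%.
- *All 15 re-treatments first, then 5 clearances.* 1-KM = 5/(34 − 15) = 5/19 = 26.3%. Aalen-Johansen = 5/34 = 14.7%.
- *2 on-treatment clearances, then 15 re-treatments, then 5 clearances.* 1-KM = 1 − (32/34)(12/17) = 33.6%. Aalen-Johansen = 7/34 = 20.6%.

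| On-treatment / follow-up clearances / re-treatments | Aalen-Johansen | 1-KM, even timing (excess in points) | 1-KM, re-treatments first (excess in points) |
|---|---|---|---|
| 0 / 1 / 2 | 2.9% | 3.0% (0.1) | 3.1% (0.2) |
| 0 / 3 / 10 | 8.8% | 10.4% (1.5) | 12.5% (3.7) |
| 0 / 5 / 15 | 14.7% | 19.4% (4.7) | 26.3% (11.6) |
| 2 / 5 / 15 | 20.6% | 25.8% (5.2) | 33.6% (13.0) |

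Excesses are computed before rounding. When all clearances precede the re-treatments, the excess is 0 in every row.

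**The case against.** The strongest reply is that this is a supplementary analysis whose label is loose, and that little depends on it. Most of that stands.

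- A reader might infer that the planned time-to-seroclearance estimate itself is inflated. It is not: the first-listed analysis does not censor at re-treatment.
- A reader might infer that the trial's off-treatment results are overstated. Those endpoints are binary, and restarted participants do not count as responders for seroclearance without NA restart or for functional cure. The censoring rule does not touch them.
- The curve should not be read as off-NA seroclearance. Time runs from first intake, so on-treatment clearance counts. Participants who miss the completion criteria "should continue NA treatment during the 48-week FU Period" (Protocol 6.5.1), stay at risk and can have events.
- It is tempting to say that re-treated participants were unlikely to clear. The documents do not establish this: Protocol 4.2 says that ALT rises after stopping NA may reflect immune activation and can lead to functional cure. If the sponsor intends a hypothetical estimand, as if NA had not been restarted, the direction of bias is not settled.
- Inflated medians for seroclearance are not shown. The highest value in the assumed range is 33.6%, so neither estimator reaches a median.
- The excess need not be largest in the arm with most re-treatment, because timing matters as well as number.
- The log-rank test with re-treatment censored remains a valid comparison of cause-specific hazards.

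What the reply does not remove is the mismatch between label and estimator. The SAP states no hypothetical estimand, and the censored variant is its only time-to-event analysis of the HBsAg endpoints that takes NA restart into account.

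**Conclusion.** The point holds for the additional variants that censor at NA re-treatment, and only for those. There, 1-KM is not the probability of reaching the event before NA restart; it equals or exceeds it. That direction follows from the algebra and needs no assumed rates. The size does: 0 to about 13 percentage points over the assumed counts and timings with 34 per arm, and nothing in the documents narrows that range. For HBsAg <100 IU/mL the effect is essentially nil, because participants who stop NA under the completion criteria have already had that event. In 5.4.1.3.2 the defect is one of wording: as written, the status of the re-treatment version of seroconversion is unclear. The correction is worth making because it is cheap and brings these curves into line with the SAP's own binary rules, but it changes no main result.

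**What to change.** 1. In 5.4.2.3, state that for every variant taking NA re-treatment into account (5.4.1.3.1, 5.4.1.3.2 and 5.5.1.3), re-treatment is a competing event, and plot the Aalen-Johansen cumulative incidence by arm with a 90% CI. If a hypothetical estimand is wanted instead, state it and drop the term cumulative incidence for that curve.
2. Keep the log-rank test, described as a comparison of cause-specific hazards. Gray's test is optional.
3. Keep the versions that ignore re-treatment as they are.
4. Rewrite the last sentence of 5.4.1.3.2 so that the re-treatment version of seroconversion is clearly an additional analysis, as in 5.4.1.3.1.

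The cost is SAP wording and a standard procedure. No new data are needed, since NA restart is already recorded on the CRF page for NA administration (SAP 5.4.1.1.2). The only downside is that the supplementary curves will be equal to or slightly lower than under the present rule.
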